13.3 Secondary and Tertiary Efficacy Endpoints

13.3.1 Annualized Bleeding Rate and FVIII Utilization

The first three secondary efficacy endpoints are:

- The change from baseline (prior to BMN 270 infusion while receiving FVIII prophylaxis) in the annualized utilization (IU/kg/year) of exogenous FVIII replacement therapy in the efficacy evaluation period (“Post-FVIII prophylaxis period”)
- The change from baseline (prior to BMN 270 infusion while receiving FVIII prophylaxis) in the annualized number of bleeding episodes irrespective of exogenous FVIII replacement treatment (annualized bleeding rate, ABR for all bleeds) in the efficacy evaluation period (“Post-FVIII prophylaxis period”)
- The change from baseline (prior to BMN 270 infusion while receiving FVIII prophylaxis) in the annualized number of bleeding episodes requiring exogenous FVIII replacement treatment (annualized bleeding rate, ABR) in the efficacy evaluation period (“Post-FVIII prophylaxis period”)

The annualized utilization (IU/kg/year) of exogenous FVIII replacement therapy is defined as

$$\frac{\text{Sum of FVIII use (IU/kg) during calculation period}}{\text{Total number of days during the calculation period}} \times 365.25$$

The annualized number of bleeding episodes (for all bleeds and treated bleeds), i.e., annualized bleeding rate (ABR for all bleeds and treated bleeds), is defined as

$$\frac{\text{Number of bleeding episodes (all bleeds or treated bleeds) during the calculation period}}{\text{Total number of days during the calculation period}} \times 365.25$$

The calculation period in the above formulas for the post-baseline value is:

- For the primary analyses, the efficacy evaluation period “Post-FVIII prophylaxis period” as defined in Section 13.1.
- For the supportive analyses, other efficacy evaluation periods as defined in Section 13.1.

If a post-baseline value is missing, e.g., when a subject drops out before Week 5, the change in ABR and annualized FVIII utilization will be imputed as the median value of the changes of all subjects’ observed cases.

The baseline values of ABR and FVIII utilization for each subject will be derived based on the 12-month historical data prior to 270-303 study screening up until the BMN 270 infusion date.

For the number of bleeding episodes, only treated bleeds will be considered. Bleeds due to surgery/procedure are not included. Only treatments that were recorded as “treatment for bleed” are included in the determination of a treated bleed. The definition of a “treated bleed” is as follows:

- If a bleed is directly followed by a hemophilia medication reported to be a “treatment for bleed” within 72 hours (or 3 calendar days if time is not available), it is considered to be a treated bleed. This bleed and the first treatment thereafter are referred to as a pair
- If multiple bleeds of different type or/and different anatomical location occur within 24 hours (of the last bleed before treatment for bleed) or on the same calendar day, the subsequent treatment within 72 hours (or 3 calendar days if time is not available) is considered to pair with each of these bleeds. Each of these bleeds that is within 72 hours (or 3 calendar days if time is not available) of the subsequent treatment is therefore considered to be a treated bleed

- Two bleeds of the same type and at the same anatomical location are considered to be one bleed if the second occurs within 72 hours (or 3 calendar days if time is not available) from the last treatment for the first bleed. The last treatment is defined as the last treatment before a new bleed occurs, either in the same or in a different location. This is regardless whether the second bleed is followed by a treatment

The changes from baseline in ABR and annualized FVIII utilization will be tested using Wilcoxon signed-rank tests (primary method) and one-sample t-tests (supportive method). Only negative changes indicate efficacy.

Supportive and sensitivity analyses on ABR (for all bleeds and treated bleeds) and annualized FVIII utilization will include:

The number of bleeding episodes and total FVIII utilization will be listed by subject and by periods (pre-BMN 270 infusion [baseline period], Weeks 1-4, Week 1 to end of original FVIII prophylaxis, and the efficacy evaluation periods as defined in [Table 13.1.1](#)). The ABR and annualized FVIII utilization (IU/kg/year) will be summarized descriptively by periods.

The changes from baseline in ABR (for all bleeds and treated bleeds) and annualized utilization (IU/kg/year) of exogenous FVIII replacement therapy will also be analyzed using data in different efficacy evaluation periods as defined in [Table 13.1.1](#).

The ABR may be analyzed using a generalized linear mixed model assuming negative binomial as the underlying distribution. The model will include period (pre-BMN 270 infusion [baseline period], Week 1-end of FVIII Prophylaxis, Post FVIII Prophylaxis-Last Visit) as the only factor. The analysis will be performed using the SAS GENMOD procedure where the duration of each period is included as an OFFSET to account for varying follow-up times and a REPEATED statement is included to account for the intra-patient comparison.

The primary analyses on ABR and FVIII utilization may be conducted for the PP population when applicable.

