5.6 Handling of Dropouts and Missing Data

If a subject withdraws from the study prematurely, the subject will be asked to complete an Early Termination Visit (ETV), the data from which will be included in summaries and analyses.

Missing dates or partially missing dates will be imputed conservatively for concomitant medications and adverse events (AEs) to ensure that an AE is considered treatment emergent when possible and the duration is the longest possible duration.

FVIII activity levels below the lower limit of quantitation (LLoQ) will be imputed as 0 IU/dL. To reduce variation caused by random fluctuation, FVIII activity will be analyzed as the median of observed values within each analysis visit window as defined in Appendix 20.1. Missing FVIII activity values will be imputed as follows.

- Dropout missing:
For subjects who discontinue from the study early, missing FVIII activity values post-discontinuation will be imputed to be 0 IU/dL through the data cutoff date for the analysis.
- Intermittent missing:
For subjects who continue the study, missing FVIII activity values (e.g., due to a missed study visit) will be imputed to be the smaller of the last prior non-missing value and the next non-missing value. In rare cases where the next value is unavailable for a subject who did not drop out, the missing value will be imputed through linear extrapolation using the last two prior non-missing values, capped at the last non-missing value.

Other missing data imputation for the primary efficacy endpoint and the secondary efficacy endpoints are specified in the corresponding analysis sections.

Other missing data will not be imputed unless otherwise stated.

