- Efficacy endpoints such as ABR, number of treated bleeds, annualized FVIII utilization, annualized FVIII infusions: will be some of the efficacy evaluation periods listed in [Table 13.1.1](#). In addition, descriptive summary will be provided in Weeks 1-4 and Week 1-end of FVIII prophylaxis (defined as end of week 4 post-BMN 270 infusion or end of FVIII prophylaxis plus 2 days for products of standard half-life or plasma-derived and 4 days for products of extended half-life, whichever is later)

Time to discontinuation of FVIII prophylaxis post-BMN 270 infusion and duration of efficacy evaluation period for primary analysis of the aforementioned efficacy endpoints will be summarized.

Table 13.1.1: Efficacy Evaluation Periods for the Analyses of Number of Bleeding Episodes, FVIII Utilization and FVIII Infusions

Efficacy Evaluation Period	Start Point	End Point	Analysis
Post-FVIII prophylaxis period	Start of Week 5 post-BMN 270 infusion or end of FVIII prophylaxis plus 3 days for products of standard half-life or plasma-derived and 5 days for products of extended half-life, whichever is later	Last visit by data cutoff	Primary, Wilcoxon signed-rank test
Post-FVIII prophylaxis – week 52	Start of Week 5 post-BMN 270 infusion or end of FVIII prophylaxis plus 3 days for products of standard half-life or plasma-derived and 5 days for products of extended half-life, whichever is later	Last visit by data cutoff or end of Week 52 post-BMN 270 infusion, whichever is earlier	Supportive, Wilcoxon signed-rank test
Post-FVIII prophylaxis – restart of prophylactic treatment up to Week 52	Start of Week 5 post-BMN 270 infusion or end of FVIII prophylaxis plus 3 days for products of standard half-life or plasma-derived and 5 days for products of extended half-life, whichever is later	Last visit by data cutoff, end of Week 52 post-BMN 270 infusion or 1 day before restart of prophylactic treatment, whichever is earlier	Supportive, Wilcoxon signed-rank test
Post-FVIII prophylaxis – restart of prophylactic treatment up to last visit	Start of Week 5 post-BMN 270 infusion or end of FVIII prophylaxis plus 3 days for products of standard half-life or plasma-derived and 5 days for products of extended half-life, whichever is later	Last visit by data cutoff or 1 day before restart of prophylactic treatment, whichever is earlier	Supportive, Wilcoxon signed-rank test

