Note: end of FVIII prophylaxis is defined as last usual FVIII prophylaxis not followed by another usual FVIII prophylaxis for at least 28 days.

Restart of prophylactic treatment means restart of FVIII or start emicizumab prophylaxis. Restart of FVIII prophylaxis is defined as the first usual FVIII prophylaxis administered at least once a week for ≥ 4 consecutive weeks. Start of emicizumab prophylaxis is defined as the first emicizumab injection among 2 or more emicizumab injections administered within 31 days.

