13.2.1 Primary Analysis for the Primary Efficacy Endpoint

The primary analysis of FVIII activity will be based on the mITT population. If any subject in the mITT population has no assessment available at Week 52, the imputation methods specified in Section 5.6 will be used to impute the missing value. Specifically, if the subject discontinues from the study prior to Week 52, the missing value will be imputed to be 0 IU/dL at Week 52; if the subject continues the study, the missing value will be imputed to be the smaller of the median value in the subject's last 4-week window prior to Week 52 containing a valid observation and the median value in the subject's next 4-week window post Week 52 containing a valid observation. If the value of the next 4-week window is unavailable (e.g., Week 52 is the last visit by the data cutoff date), the missing value will be imputed through linear extrapolation using the median values in last two 4-week windows prior to Week 52 containing a valid observation, capped at the value in the last 4-week window.

A listing of subjects with no assessment available at Week 52 will be provided, including the imputed value and associated analysis visit window as well as the next available FVIII activity value after Week 52 and associated analysis visit window, if available. This is to assess potential bias in missing data imputation.

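### Section 13.3.1 imputes a missing change in ABR or FVIII use as the median observed change, which understates variability and leans toward benefit; by the period definitions the rule would also cover a subject who never stops prophylaxis

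*SAP*

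**What the plan says.** All references are to SAP version 2.0.

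- **The imputation (Section 13.3.1).** The rule opens "If a post-baseline value is missing, e.g., when a subject drops out before Week 5, the change in ABR and annualized FVIII utilization will be", and the imputed value is fixed in these words: "the change in ABR and annualized FVIII utilization will be imputed as the median value of the changes of all" subjects with observed data. Dropping out before Week 5 is an example of the trigger, not its limit.
- **The period (Section 13.1, Table 13.1.1).** The post-baseline value is computed only over the Post-FVIII prophylaxis period. Its start is the later of two dates: "Start of Week 5 post-BMN 270 infusion or end of FVIII prophylaxis plus 3 days for products of standard half-life or plasma-derived" (5 days for extended half-life products). It runs to the last visit by data cutoff.
- **End of prophylaxis (note to Table 13.1.1).** The "end of FVIII prophylaxis is defined as last usual FVIII prophylaxis not followed by another usual FVIII prophylaxis for at least 28 days".
- **The test (Section 13.3.1).** Wilcoxon signed-rank is primary and the one-sample t-test is supportive. On direction: "Only negative changes indicate efficacy".
- **The contrast (Sections 5.6 and 13.2.1).** For FVIII activity, "missing FVIII activity values post-discontinuation will be imputed to be 0 IU/dL through the data cutoff date for the analysis". For a subject who discontinues before Week 52, "the missing value will be imputed to be 0 IU/dL at Week 52".

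**The concern.** A single imputation at the centre of the observed changes has two effects. It removes variability, because each imputed subject adds a value but no spread. It also assumes that a subject without a value did as well as the typical subject with one. For FVIII activity the same plan makes the opposite assumption about dropouts.

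The subject who never stops prophylaxis makes the second effect concrete. Without a 28-day gap there is no end of prophylaxis, so there is no evaluation period and no post-baseline value. Read literally, the rule credits a subject who is still infusing routinely with the typical fall in FVIII use. That consumption has been recorded; the period definition sets it aside.

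All four periods in Table 13.1.1 share the same start and differ only in their end. FVIII used between Day 33 and a late stop therefore enters none of the planned signed-rank tests. Section 13.3.1 names no observed-case or no-change check of the imputation.

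**Working it through.** **Inputs.** The number dosed is 22 (Section 4.5). The primary efficacy population is mITT (Section 5.1), whose size is not stated, so N = 22 is an assumption. The number of subjects with no post-baseline value is not stated either; k = 1, 2, 3 is an assumed range.

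**The plan's own figure.** The SAP gives no figure for this imputation. Its only design figure is 85% power for the primary endpoint (n = 16, effect size 0.8, one-sided 0.025). With a noncentral t on 15 df and noncentrality 0.8 × √16 = 3.2, power is 0.848, so the figure reproduces. It does not bear on this point.

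**Step 1: does the rule reach a subject who never stops?** There is no 28-day gap, so no end of prophylaxis, no start of the period and no calculation period for the annualized formula. The value is missing and the open-ended trigger applies. The alternative is to take the last infusion before cutoff as the end. The period would then be empty or a few days long, which is no better. The SAP does not say which reading is meant.

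**Step 2: shift in the mean.** Let m be the mean and M the median of the N − k observed changes.

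- Median imputation: [(N − k)m + kM]/N
- True change of 0 in the imputed subjects: (N − k)m/N
- Difference: (k/N) × M

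| k | k/22 | k/20, if mITT were 20 |
|---|---|---|
| 1 | 4.5% | 5.0% |
| 2 | 9.1% | 10.0% |
| 3 | 13.6% | 15.0% |

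The percentages are shares of the median change.

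**Step 3: type I error, continuous changes (the FVIII-use case).** Simulation with N = 22, Normal(0, 1) changes, k of them replaced by the observed median, two-sided 5%, 10,000 runs:

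| k | Wilcoxon | t-test | Wilcoxon, range over repeat simulations |
|---|---|---|---|
| 1 | 6.2% | 5.7% | 6.1–6.6% |
| 2 | 8.7% | 7.9% | 8.2–9.3% |
| 3 | 10.5% | 8.8% | 10.4–10.9% |

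With a change of 0 imputed instead, the Wilcoxon rate is about 5%. This inflation comes from the lost variance and needs no informative dropout.

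**Step 4: rejection when there is an effect.** With a standardized effect of 0.5 in the observed subjects and 4,000 runs per setting, Wilcoxon rejection under median imputation against a change of 0 is 62.0% v 57.3% (k = 1), 62.0% v 52.9% (k = 2) and 66.3% v 52.8% (k = 3).

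**Step 5: type I error, low counts (the ABR case).** Assumed gamma-Poisson counts, equal follow-up, n = 22:

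| Mean bleeds per period | k = 1 | k = 2 | k = 3 |
|---|---|---|---|
| 0.5 | 4.4% | 4.8% | 4.5% |
| 1 | 5.2% | 5.5% | 5.6% |
| 2 | 5.3% | 6.2% | 7.3% |

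With low counts the median change under no effect is often exactly 0, and the signed-rank test drops zeros, so the copies of the median add little.

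**The case against.** A reader might infer that treatment failures in general are counted as typical successes. The documents do not support that.

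- A subject who stops, loses expression and restarts is counted in full. The primary period runs to the last visit and is not cut at restart.
- Dropping out before Week 5 is not evidence of failure, since Section 13.1 has prophylaxis continuing for the first 4 weeks.
- The case of the subject who never stops is inferred from the period definition and the open-ended trigger. It is not written in the SAP, and nothing shows that any subject was in that position.
- Baseline ABR was measured on prophylaxis, so the median ABR change could be near 0 and the imputed value need not look like a success.

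Nor would the problem be invisible. Section 13.3.1 lists bleeds and FVIII use by subject and period, including Week 1 to the end of original prophylaxis, and summarizes the rates by period. Section 13.1 summarizes time to stopping prophylaxis and the length of the evaluation period. The optional negative binomial model for ABR keeps the time before stopping as its own period.

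These points limit the concern without removing it. Listings and summaries would show a late or absent stop, but they would not correct the estimated change or its p-value. The contrast with 0 IU/dL stands for dropouts only, because that rule does not address subjects who stay in the study on prophylaxis.

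**Conclusion.** The point holds within limits. The median rule understates variability whenever it is used. It also favours benefit whenever the imputed subjects' true change is less favourable than the median. It would apply to a subject who never stops prophylaxis, even though that subject's FVIII use is observed.

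For FVIII use, with 1 to 3 of an assumed 22 subjects imputed, Wilcoxon type I error is about 6% to 11%. If their true change is 0, the mean reduction is overstated by 4.5% to 13.6% of the median change. For ABR, the inflation is small at a mean of 1 to 2 bleeds per period (about 5% to 7%) and absent at 0.5.

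These sizes rest on the assumed k, N and distributions. The primary endpoint is untouched. The severity is should-fix, confined to secondary endpoints.

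**What to change.** 1. In Section 13.3.1, state that a subject who never meets the end-of-prophylaxis definition has annualized FVIII use computed from observed data from Day 33 to the last visit. Report ABR over the same days, labelled as including time covered by prophylaxis.
2. For a subject with no data after Day 32, replace the median with a change of 0.
3. Report an observed-case analysis alongside. The signed-rank test drops zeros, so its p-value will match the zero-change analysis for these subjects; the mean and the t-test will differ. A change of 0 is itself an untestable assumption, which is why both should be shown.
4. Add one supportive row to Table 13.1.1 with a Day 33 start for every subject, so that FVIII used before a late stop enters a change analysis.

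The cost is some SAP wording, the observed-case results and one extra supportive period. The estimated reductions may be slightly less favourable. ABR from Day 33 mixes time on and off prophylaxis and must be read that way. If no subject is missing a value, items 1 to 3 change no result.

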13.1 Efficacy Evaluation Periods

To avoid breakthrough bleeding, subjects only discontinued exogenous prophylactic FVIII replacement therapy after 4 weeks following infusion of BMN 270. Four weeks represents the time by which endogenous production of FVIII following gene transfer is expected to be efficacious, based on earlier results.

For the primary data analysis, the efficacy evaluation period for

- Efficacy endpoints such as ABR (all bleeds and treated bleeds), number of bleeds (all bleeds and treated bleeds), annualized FVIII utilization, annualized FVIII infusions and PROs: will be defined as starting from Week 5 post-BMN 270 infusion (Study Day 33) or the end of FVIII prophylaxis plus the washout period (3 days for products of standard half-life or plasma-derived and 5 days for products of extended half-life), whichever is later, until subjects complete the study, reach the last visit by data cutoff for the analysis, or withdraw from the study (ETV), whichever is the earliest
- Efficacy endpoint of FVIII activity based on chromogenic substrate assay: will be defined as starting from Week 5 post-BMN 270 infusion (Study Day 33) until subjects complete the study, reach the last visit by data cutoff for the analysis, withdraw from the study (ETV) (FVIII activities post withdrawal will be imputed to be 0 IU/dL through the data cutoff date for the analysis), or resume routine FVIII prophylaxis (should that occur) (restart of FVIII prophylaxis is defined as the first usual FVIII prophylaxis administered at least once a week for ≥ 4 consecutive weeks), whichever is the earliest
- Efficacy endpoint of FVIII activity based on one-stage assay: will be defined as starting from Week 5 post-BMN 270 infusion (Study Day 33) until subjects complete the study, reach the last visit by data cutoff for the analysis, resume routine FVIII prophylaxis or start emicizumab prophylaxis (should that occur) (start of emicizumab prophylaxis is defined as the first emicizumab injection among 2 or more emicizumab injections administered within 31 days), whichever is the earliest.

For supportive data analyses, the efficacy evaluation period for

- Efficacy endpoint of FVIII activity: will be defined as from BMN 270 infusion to until subjects complete the study, reach the last visit by data cutoff for the analysis, or withdraw from the study (ETV), whichever is the earliest

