14.1 Adverse Events

Only treatment-emergent adverse events (TEAEs) occurring and reported during the study period will be included in the adverse event summaries. A TEAE is defined as any AE that newly appeared or worsened in severity following initiation of study drug administration. Adverse events will be coded in accordance with MedDRA.

An adverse drug reaction (ADR) is any AE for which there is a reasonable possibility that the study drug caused the AE. The investigator will assess the causality for individual AEs, applying the guidance specified in protocol, and those assessed as IP-related will be considered ADRs.

A serious adverse event (SAE) is any untoward medical occurrence that at any dose meets one or more of the seriousness criteria enumerated in the protocol. AE severity, not equivalent to seriousness, will be assessed using the protocol defined categories using the NCI CTCAE v4.03.

All bleeding events and suspected bleeding events, regardless of the need for exogenous FVIII therapy as treatment, should be captured in subject diaries and recorded on the designated bleeding electronic case report form (eCRF). Bleeding events and suspected bleeding events should not be reported as adverse events, with the following exception:

- All bleeding events and suspected bleeding events which meet one or more of the criteria for being serious (refer to the protocol Section 10.2) should be reported as serious adverse events (whether or not they are bleeding events that are normal sequelae of hemophilia, and whether or not they require exogenous FVIII as treatment).

The study AE reporting period is as follows: After informed consent but prior to initiation of study treatment, only SAEs associated with any protocol-imposed interventions will be reported. After informed consent is obtained and following the administration of study drug, the reporting period for all non-serious AEs and SAEs begins and continues for approximately 5 years or until study discontinuation/termination.

The following types of AEs will be summarized: all AEs, AEs assessed by investigator as related to BMN 270, SAEs, SAEs assessed by investigator as related to BMN 270, AEs leading to study discontinuation, deaths, and events of special interest (EOSI), AEs associated with corticosteroid use or non-steroidal immunosuppressant use, and AEs reported as laboratory abnormalities with clinical significance. Listings will be provided.

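### SAP Section 13.3.1 restricts the bleed count to treated bleeds without saying for which endpoint, which contradicts the all-bleeds ABR secondary endpoint

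*SAP*

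**What the plan says.** Section 13.3.1 of the SAP (version 2.0) lists two bleeding endpoints among the first three secondary endpoints. One is the change from baseline in the "annualized number of bleeding episodes irrespective of exogenous FVIII replacement treatment (annualized bleeding rate, ABR for all bleeds"). The other is the change in the "annualized number of bleeding episodes requiring exogenous FVIII replacement treatment (annualized bleeding rate, ABR"). One formula serves both, with the numerator given as "Number of bleeding episodes (all bleeds or treated bleeds) during the calculation period".

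The text on deriving bleeds follows the formula and opens with "For the number of bleeding episodes, only treated bleeds will be considered". It next excludes bleeds due to surgery or procedures, then defines a treated bleed by pairing and merging rules. Under the merging rule, two bleeds of the same type and place "are considered to be one bleed if the second occurs within 72 hours" of the final treatment given for the first one. The rule adds that it does not matter whether the second bleed was treated.

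Changes in both ABRs are tested with the Wilcoxon signed-rank test as the primary method. The same sentence stands in version 1.0 and was carried over unchanged.

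**The concern.** The sentence uses the same term for what is counted as the ABR formula does, and nothing ties it to the treated-bleeds endpoint. A programmer who follows it as a derivation rule would leave untreated bleeds out of the endpoint defined to include them.

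What is at stake is one tested secondary endpoint in an open-label, single-arm study. By its definition, the all-bleeds ABR does not depend on whether a bleed was treated with FVIII, whereas the treated-bleeds ABR does. That is the information the second count adds (this is my reasoning; the SAP gives no rationale), and it is what the sentence, read literally, removes.

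**Working it through.** The SAP gives no expected bleed counts and no power for either ABR, so there is no planned figure to reproduce. Its one power statement, in Section 4.5, concerns FVIII activity and is not affected. The check is therefore a comparison of text, followed by a literal application of the rule.

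**1. The texts side by side (SAP version 2.0)**

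| Place | What is counted |
|---|---|
| 13.3.1, endpoint list | all bleeds and treated bleeds, as separate endpoints |
| 13.3.1, ABR formula | all bleeds or treated bleeds |
| 13.3.1, derivation text | treated bleeds only, no endpoint named |
| 13.3.1, supportive analyses | "Supportive and sensitivity analyses on ABR (for all bleeds and treated bleeds) and annualized FVIII utilization will include" |
| 13.1, primary evaluation period | "number of bleeds (all bleeds and treated bleeds") |
| 9, baseline characteristics | baseline ABR for treated bleeds and for all bleeds, listed separately |
| 13.5, subgroups | ABR for both |

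The derivation sentence is the only one of the seven that leaves out untreated bleeds while purporting to cover the bleed count in general. The data for the wider count are collected. Section 14.1 says "All bleeding events and suspected bleeding events, regardless of the need for exogenous FVIII therapy as treatment, should be captured in subject diaries" and entered on a dedicated bleeding case report form.

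**2. Literal application**

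For each subject, let T be the number of treated bleeds, U the number of untreated bleeds and D the number of days in the period.

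- Intended: all-bleeds ABR = (T + U) / D × 365.25; treated-bleeds ABR = T / D × 365.25.
- Under the sentence as written: both equal T / D × 365.25.

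For illustration, take the longest possible post-prophylaxis period to Week 52, Days 33 to 368 (Appendix 20.1): D = 368 − 33 + 1 = 336. The primary period runs on to the last visit by data cutoff, so its D may differ. The bleed counts are assumptions.

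| T | U | All-bleeds ABR, intended | Treated-bleeds ABR | All-bleeds ABR under the sentence |
|---|---|---|---|---|
| 1 | 0 | 1.09 | 1.09 | 1.09 |
| 1 | 1 | 2 / 336 × 365.25 = 2.17 | 1.09 | 1.09 |
| 1 | 3 | 4 / 336 × 365.25 = 4.35 | 1.09 | 1.09 |
| 0 | 2 | 2.17 | 0 | 0 |

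If the sentence is applied at baseline and post-baseline, each subject has the same change on both endpoints, so the Wilcoxon statistic and p-value also coincide. The direction of the error in the change from baseline cannot be given, because untreated bleeds would be missing from both periods in unknown numbers.

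**3. What remains open once the sentence is limited**

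- The surgery/procedure exclusion comes directly after the treated-only sentence. The text does not say whether it also governs the all-bleeds count.
- The merging rule takes its 72 hours from treatment of the first bleed. It covers a treated first bleed followed by a treated or untreated repeat. It has no starting point when the first bleed was untreated.

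**The case against.** The strongest reply is that no careful reader would apply the sentence to the all-bleeds ABR. It leads into the definition of a treated bleed, which is its natural scope, and every other place in the table above asks for both counts or names the all-bleeds endpoint outright. This stands as evidence of intent. A reader might infer that the trial will report one endpoint twice, but the documents do not support that as a prediction. It would happen only if one sentence overrode the rest of the plan. What the reply does not remove is that the sentence is unscoped and conflicts with the formula it follows.

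A reader might also infer that the merging rule fails for untreated bleeds altogether. It does not: an untreated repeat soon after a treated first bleed is expressly merged. The gap is confined to an untreated first bleed.

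Nor does the SAP support saying that repeat diary entries for one untreated bleed would count as separate bleeds. Section 14.1 has bleeds recorded on a case report form as well as in diaries, and does not say that each diary entry becomes a separate bleed. Instructions for recording an episode may sit in the protocol or the form's guidance, neither of which is shown.

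Finally, the reply that only one secondary endpoint is touched is correct. FVIII activity, FVIII utilization and treated-bleeds ABR are unaffected.

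**Conclusion.** The contradiction is real and is in the current text. As written, the sentence gives a wrong all-bleeds ABR for any subject with an untreated bleed in the period, and makes the two ABRs identical for all subjects. How much this would shift the trial's result cannot be stated, because the SAP gives no number of untreated bleeds and the ABR values above rest on assumed counts.

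The rest of the SAP makes the intended count recoverable, so this is a point that should be fixed rather than one that undermines the analysis. No sample size, power or significance level changes.

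**What to change.** In Section 13.3.1, limit the treated-only sentence to ABR for treated bleeds. State that ABR for all bleeds counts all recorded bleeds whether or not they were treated, in both the baseline and the post-baseline period.

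In the same edit, the sponsor should state whether the surgery/procedure exclusion applies to the all-bleeds count, and how repeat bleeds are counted when the first was untreated. The SAP offers no basis for preferring a particular merging rule in that case, so none is proposed here. If the protocol or the case report form guidance already settles either question, a cross-reference is enough.

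The cost is a few sentences in the SAP and a check of the derivation program. No new data are needed.
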